## **RANDOMIZATION:**

Once a subject meets all the inclusion and exclusion criteria, they will be assigned a randomization number on day 0/baseline. Enrolled subjects will be randomized in a 2:1 ratio of Duobrii to placebo.

The randomization will be performed by designated research staff/personnel at the Icahn School of Medicine using a randomization generator. The subjects and assessors (sub-investigators) will remain blinded to individual treatment assignment during the study. Research staff will also be responsible for blinding of the medication.

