## **DATA ANALYSIS:**

### **Sample Size Considerations**

A sample size of n=20 Duobrii-treated subjects allows 80% power at 5% significance to detect a minimum reduction of 35% in the median number of lesions at week 12 with the one-sided Wilcoxon nonparametric test. This calculation assumes an average count of 15 AKN lesions at baseline and a standard deviation of 7 lesions around the mean difference at week 12, and a drop-out rate of 30%. These numbers are based on data reported by Okoye et al. (2014), who compared lesion counts at week 16 to baseline in a set of 11 UVB-treated subjects. The sample size calculation is based on the asymptotic relative efficiency of the Wilcoxon test compared to paired Student's t-test. A sample size of n=20 treated subjects compared to n=10 placebo-treated ones allows 80% power at 5% significance to detect a minimum 50% difference between proportions of patients with a reduced number of AKN lesions. This calculation is based on the application of a one-sided Z-test for the difference between two independent proportions and also assumes a maximum 30% dropout rate within each arm.

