## **Primary Endpoint**

The primary analysis for the primary endpoint will test for a reduction in lesion counts after 12 weeks of treatment. We will apply the two-sided Wilcoxon test to assess the significance of the difference between pre- and post-treatment median numbers of lesion counts. The secondary analysis will compare the reduction in lesion counts between active and placebo groups after 12 weeks. For this purpose, we will apply the Z-test to verify the hypothesis that the proportions of patients with reduced AKN lesions differ between active and placebo groups. A more comprehensive analysis will adjust a generalized linear mixed-effects model, based on Poisson distribution, including time and treatment group as fixed factors and a random intercept for each subject. This model will include the whole time-course and contrasts of interests will be estimated.

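### The between-arm Z-test on lesion response is powered as one-sided at 5%, but the analysis section words it without direction and gives neither side nor alpha; read as two-sided, the stated 80% power mostly does not hold

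*Combined protocol and SAP*

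**What the plan says.** Sample Size Considerations gives the between-arm calculation. The arms are described as "A sample size of n=20 treated subjects compared to n=10 placebo-treated ones", and the plan states that this "allows 80% power at 5% significance to detect a minimum 50% difference between proportions of patients with a reduced number of AKN lesions". It continues: "This calculation is based on the application of a one-sided Z-test for the difference between two independent proportions". The calculation "also assumes a maximum 30% dropout rate within each arm". No response rate is given for either arm, and the variance formula is not named.

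The Primary Endpoint section under Data Analysis places this comparison second to the pre/post test: "The secondary analysis will compare the reduction in lesion counts between active and placebo groups after 12 weeks". It then states: "we will apply the Z-test to verify the hypothesis that the proportions of patients with reduced AKN lesions differ between active and placebo groups". No side and no alpha are attached to the Z-test there.

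The pre/post Wilcoxon test is sized on a "minimum reduction of 35% in the median number of lesions at week 12 with the one-sided Wilcoxon nonparametric test", but the Primary Endpoint section labels that same test two-sided. No section reconciles the sizing with the analysis for either test.

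**The concern.** A one-sided test at 5% rejects when z exceeds 1.645. A two-sided test at 5% requires 1.960. A hypothesis that two proportions differ has no direction, and its usual test is two-sided. The section that sets the power and the section that defines the analysis therefore point to different decision rules for the same comparison.

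Two things are at stake. First, a result with z between 1.645 and 1.960 is significant under one rule and not under the other, and with the side left open the choice could be made after the data are seen. Second, the stated 80% power belongs to the one-sided test, not to the test as the analysis section words it.

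The comparison matters although it is labelled secondary. The Primary Hypothesis is improvement relative to placebo, which the pre/post Wilcoxon test does not address, and the Z-test is the only between-arm analysis of lesion response with a stated power.

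**Working it through.** **Inputs from the documents.** 20 active and 10 placebo (Sample Size Considerations; the 2:1 ratio is repeated under Randomization); dropout 30% per arm, so 20 × 0.7 = 14 and 10 × 0.7 = 7 completers; alpha 5%; power 80%; difference 50%, taken as 50 percentage points.

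**Assumption.** The arm rates are not given. I use 75% active and 25% placebo, then vary the placebo rate from 5% to 49% with the difference held at 50 points.

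**1. Reproducing the stated 80% (one-sided, unpooled variance).**
- SE₁ = √(0.75 × 0.25/14 + 0.25 × 0.75/7) = 0.2004, and 0.5/0.2004 = 2.495.
- Power = Φ(2.495 − 1.645) = Φ(0.850) = 0.802.
- Solving for size: placebo n = [0.1875 + 0.1875/2] × (1.645 + 0.842)²/0.5² = 6.96, rounded up to 7, with 14 active. Dividing by 0.7 gives 10 and 20, the plan's own numbers.

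So the stated 80% fits a one-sided 5% test with unpooled variance. With pooled variance under the null, the one-sided figure at these rates is 0.733.

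**2. The same design, two-sided at 5%.**
- Unpooled: Φ(2.495 − 1.960) = Φ(0.535) = 0.703.
- Pooled: the pooled rate is (14 × 0.75 + 7 × 0.25)/21 = 0.583; SE₀ = √(0.583 × 0.417 × (1/14 + 1/7)) = 0.228; power = Φ((0.5 − 1.960 × 0.228)/0.2004) = 0.604.

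**3. Range over the unknown rates (14 versus 7, 50-point difference).**

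| Placebo / active | One-sided, unpooled | Two-sided, unpooled | Two-sided, pooled |
|---|---|---|---|
| 5% / 55% | 0.940 | 0.892 | 0.647 |
| 10% / 60% | 0.893 | 0.823 | 0.614 |
| 15% / 65% | 0.853 | 0.768 | 0.599 |
| 20% / 70% | 0.822 | 0.729 | 0.596 |
| 25% / 75% | 0.802 | 0.703 | 0.604 |
| 35% / 85% | 0.790 | 0.688 | 0.649 |
| 45% / 95% | 0.815 | 0.719 | 0.739 |
| 49% / 99% | 0.835 | 0.746 | 0.790 |

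Unpooled, two-sided power reaches 80% only at the two lowest placebo rates shown. Pooled, it never does.

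**4. Difference detectable with 80% two-sided power (rates symmetric about 50%).**
- Unpooled: d/√[((1 − d²)/4) × (3/14)] = 1.960 + 0.842 gives d = 0.544, about 54 points.
- Pooled: d = 1.960 × SE₀ + 0.842 × SE₁. At d = 0.60 (80% versus 20%) the right-hand side is 1.960 × 0.2268 + 0.842 × 0.1852 = 0.600, so about 60 points.

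**5. Results that change sides.**
- Pooled statistic, 10/14 versus 2/7: difference 0.4286, pooled rate 12/21, SE 0.2291, z = 1.871; one-sided p = 0.031, two-sided p = 0.061. The outcome 8/14 versus 1/7 gives the same z.
- The example depends on the variance. Unpooled, 10/14 versus 2/7 has SE = √(0.2041/14 + 0.2041/7) = 0.2091 and z = 2.05, which passes both rules. The unpooled statistic has its own borderline cases: 9/14 versus 2/7 has difference 0.3571, SE = √(0.2296/14 + 0.2041/7) = 0.2134 and z = 1.67.
- By exact enumeration at 75% versus 25%, z falls between the cut-offs in 9.2% of trials (pooled) or 10.1% (unpooled). For the pooled statistic this runs from about 0 to 12% over placebo rates of 5% to 49%.

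**The case against.** The best defence is that the analysis section never calls the Z-test two-sided. The only side stated for it anywhere is one-sided, and the Primary Hypothesis is directional, so the sizing section may supply what the analysis section leaves out. On that reading this is an omission, not a contradiction. It stands this far: the two-sided reading is an inference from the non-directional wording, and the pass/fail conflict also assumes that the 5% in the sizing section, the only alpha in the documents, carries over. It does not remove the point. The Wilcoxon test is one-sided in the sizing and explicitly two-sided in the analysis, so the sizing section demonstrably does not govern the side of the analysis.

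Two stronger readings are tempting, and the documents do not support them:
- A reader might infer that the Z-test is the only Duobrii-versus-placebo analysis of lesion counts. It is not: the same section plans a Poisson mixed model with treatment group as a fixed factor, from which contrasts are to be estimated.
- A reader might infer that the Z-test carries over to the secondary outcomes. The Secondary Endpoints section reuses only the nonparametric tests of the primary endpoint; the plan calls only the Wilcoxon test nonparametric, and no responder cut-off is defined for those outcomes.

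It is also fair to object that no single power figure can be fixed without the response rates and the variance formula. That stands, so the size is given as a range.

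**Conclusion.** The point holds as a mismatch between a one-sided sizing and a non-directional analysis statement that lacks both side and alpha. It does not hold as two explicitly opposed rules.

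If the analysis is two-sided at 5%, the stated 80% power for 50 points is not delivered in most cases. At 75% versus 25% the shortfall is about 10 percentage points on the unpooled formula (80.2% to 70.3%). The pooled figure of 60.4% is about 20 points below the stated 80%, but part of that gap comes from the variance formula, since pooled power is already 73.3% one-sided. These figures rest on 14 and 7 completers, an absolute 50-point difference, the normal approximation and assumed rates. At placebo rates of 10% or less with unpooled variance, two-sided power still exceeds 80%.

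The point should be corrected before unblinding. It concerns a secondary analysis of the primary endpoint and does not threaten the design.

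**What to change.** State the side and alpha of the Z-test once, and use them in both Sample Size Considerations and the Primary Endpoint analysis. Two-sided 5% matches the wording of the hypothesis and the two-sided Wilcoxon test beside it. Declaring the test one-sided in both places would also make the text consistent, but then the hypothesis must be reworded with a direction. Settle the side of the Wilcoxon test in the same edit.

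If two-sided is chosen, keep 20 versus 10. In Sample Size Considerations, name the assumed response rates and the variance formula, and use the same formula for the test statistic. Then restate either the power for 50 points (about 70% unpooled or 60% pooled at 75% versus 25%) or the difference detectable with 80% power (about 54 points unpooled or 60 pooled, symmetric about 50%).

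The cost is two sentences and a less favourable stated power, with no change to enrolment, visits or data collection.

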## **Secondary Endpoints**

We will compare the improvement in the severity of AKN symptoms, degree of dyspigmentation, and patient-reported outcomes (DLQI and NRS) between time points (Baseline, 4, 8, and 12 Weeks) and groups (placebo and active) with the nonparametric tests described for the primary endpoint. We will also adjust, for each outcome, a generalized linear mixed-effects model including time, treatment group, their interaction as fixed effects, and a random intercept for each participant. This modeling strategy will decide each outcome's probabilistic distribution and link function based on goodness-of-fit criteria. The Spearman correlation coefficient will measure the association between reduction in lesion counts and improvement in patient-reported outcomes. In addition, we will compare the percent area of the treatment area affected with dyspigmentation (hypo- or hyperpigmentation) at each visit.

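### The supportive lesion-count mixed model is written without a time-by-treatment interaction, so fitted as written with baseline included it cannot show a between-arm difference in lesion reduction

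*Combined protocol and SAP*

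**What the plan says.** The Primary Endpoint section of Data Analysis sets out three analyses of lesion counts.

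- A Wilcoxon test of pre- against post-treatment counts.
- A between-arm comparison, introduced by "The secondary analysis will compare the reduction in lesion counts between active and placebo groups after 12 weeks" and carried out as a Z-test on the proportions of patients whose count fell.
- A Poisson mixed model, "based on Poisson distribution, including time and treatment group as fixed factors and a random intercept for each subject". Of this model the section adds: "This model will include the whole time-course and contrasts of interests will be estimated". It names neither the contrasts nor the visits.

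The Secondary Endpoints section describes a mixed model for symptoms, dyspigmentation, DLQI and NRS as "including time, treatment group, their interaction as fixed effects, and a random intercept for each participant". It lists the time points as baseline and weeks 4, 8 and 12. Lesion count is not among the outcomes of that model.

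No other section gives the lesion-count model an interaction, a baseline covariate or a baseline constraint. The schedule in Appendix A has lesion counts at baseline and weeks 4, 8 and 12, and also at the week-14 follow-up.

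**The concern.** The Primary Hypothesis is a comparison with placebo. For lesion counts, the Wilcoxon test is a pre/post comparison, and the Z-test uses only whether a patient's count fell, not by how much. The mixed model is therefore the only planned between-arm analysis that uses the size of the counts.

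A treatment effect in a randomised trial with a baseline visit is a difference between arms in how the outcome changes. In a model with time and group main effects only, that difference is carried by a term that is absent. Followed literally, the analysis would report one group ratio averaged over visits that include baseline, where treatment cannot yet have acted. It would also credit vehicle with the same proportional fall as active. Because the plan spells the term out for the secondary outcomes and leaves it out for the primary one, a programmer could reasonably fit the two models differently.

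**Working it through.** **The plan's own figures.** The plan gives no effect, power or sample size for this model, so there is none to reproduce. The illustration borrows from Sample Size Considerations, where the stated n=20 for the one-sided Wilcoxon test does reproduce. The fall is 0.35 × 15 = 5.25 with SD 7, which needs 13 by paired t-test; 13/0.955 = 13.6; 13.6/0.70 = 19.4, so 20.

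**Inputs from the documents.** "This calculation assumes an average count of 15 AKN lesions at baseline"; a "minimum reduction of 35% in the median number of lesions at week 12", giving 15 × 0.65 = 9.75; and "Enrolled subjects will be randomized in a 2:1 ratio of Duobrii to placebo", that is 20 and 10.

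**Assumed, not in the documents.** Complete data, the 35% applied to the mean, a flat vehicle arm at 15, and the onset shapes.

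**Step 1, algebra.** As written, log μ = α + τ(t) + γ·group + b(subject).
- Active minus vehicle is γ at every visit, baseline included.
- Change from baseline to week 12 is τ(12) − τ(0) in both arms, so the between-arm difference in change is 0 by construction.
- With an interaction δ(t), taking baseline as reference, that difference becomes δ(12), and exp δ(12) is the week-12 ratio of rate ratios.

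This step needs no numerical assumption.

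**Step 2, what γ estimates.** With complete data the likelihood splits into each subject's total count, which carries γ, and the split of that total across visits, which carries the time effects. So exp γ targets (sum of active means)/(sum of vehicle means) over the visits in the model.

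**Step 3, numbers.** The true week-12 ratio is 9.75/15 = 0.65.

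| Visits modelled | Full effect from week 4 | Linear onset | Effect only from week 12 |
|---|---|---|---|
| Baseline, 4, 8, 12 | 44.25/60 = 0.74 | 49.5/60 = 0.83 | 54.75/60 = 0.91 |
| The same plus week 14 at 9.75 | 54/75 = 0.72 | 59.25/75 = 0.79 | 64.5/75 = 0.86 |
| Weeks 4, 8, 12 only | 29.25/45 = 0.65 | 34.5/45 = 0.77 | 39.75/45 = 0.88 |

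The linear active means are 15, 13.25, 11.5 and 9.75.

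**Step 4, the common fall.** Whenever baseline is modelled, both arms receive the pooled week-12/baseline ratio: (20 × 9.75 + 10 × 15)/(30 × 15) = 345/450 = 0.767. That is a 23% fall in each arm for every onset shape, when the assumed truth is 35% and 0%.

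**Step 5, sensitivity (four visits, linear onset).**
- Vehicle falls 10%: true 9.75/13.5 = 0.72, written 49.5/57 = 0.87.
- Vehicle falls 20%: true 9.75/12 = 0.81, written 49.5/54 = 0.92.
- Flat vehicle, active baseline 10% lower or higher by chance: written 44.55/60 = 0.74 or 54.45/60 = 0.91, while the ratio of rate ratios stays 0.65.

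**Step 6, simulation.** Maximum-likelihood fits to 300 simulated trials per onset shape (20 against 10, four visits, subject-level log-SD 0.4) gave mean written ratios of 0.752, 0.833 and 0.912, in the table's column order. The second used visit ratios of 0.88, 0.77 and 0.65. With the interaction, the week-12 ratio of rate ratios averaged 0.655, 0.645 and 0.643.

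**Step 7, precision (linear onset, four visits, no extra-Poisson variation).**
- Ratio of rate ratios: the subject effect cancels. The log variance is about 1/195 + 1/300 + 1/150 + 1/150 = 0.0218, so SE 0.15.
- Written group ratio: the log variance is about σ²(1/20 + 1/10) + 1/990 + 1/600. At subject log-SD σ = 0.3, 0.5 and 0.7 the SE is about 0.13, 0.20 and 0.28.

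**The case against.** The strongest reply is that the wording is shorthand. The section lists factors rather than every model term, promises contrasts, and is followed at once by a fuller description of the same kind of model. That may be what was meant, and the point is therefore about the written plan, not a prediction of what will be run. But the text does not say it, and leaving the term open allows the model to be settled after the data are seen.

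Second, the week-12 between-arm question is assigned to the Z-test, not to this model. That is correct, and the plan promises no week-12 contrast from the model. It does not rescue a model that, with baseline included, can show no differential change at any visit.

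Third, the visits are not fixed. Including baseline is the natural reading of a whole time-course, but it is not stated. With post-baseline visits only and a full effect from week 4, the written ratio is 0.65, with no dilution. It still cannot vary by visit, and it then carries no change from baseline.

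Fourth, the ratios rest on complete data although 30% dropout is planned for, and they use a minimum detectable reduction in a median as if it were a mean fall. Both caveats stand for the sizes; neither touches Step 1.

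A reader might infer that the trial has no between-arm test of lesion counts, or that its primary analysis or sample size is undermined. The documents do not support that: the Z-test is between-arm, and none of the Wilcoxon test, the Z-test or the sample size depends on this model.

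**Conclusion.** The point holds for the model as written. Fitted with baseline among the visits, it cannot express a between-arm difference in lesion reduction; this follows from the model terms alone.

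The size of the distortion is illustrative and depends on the visit set and onset shape. For a true week-12 ratio of 0.65, the single ratio would be 0.74 to 0.91 with four visits, 0.72 to 0.86 with week 14 added, and 0.65 to 0.88 with post-baseline visits only. Severity is modest: the analysis is supportive, and a one-clause omission may be all that is wrong.

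**What to change.** In Data Analysis, Primary Endpoint:

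1. Write the fixed effects of the lesion-count model as time, treatment group and the time-by-treatment interaction, matching the Secondary Endpoints section.
2. Name the week-12 versus baseline active-versus-vehicle ratio of rate ratios as the contrast of interest, reported with its confidence interval.
3. State which visits enter the model, including whether the week-14 count does.

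The cost is one or two sentences and three extra parameters, or four if week 14 enters. No new data are needed. A loss of precision should not be assumed: by Step 7 the interval for the new contrast may be wider or narrower than that of the written group ratio, depending on between-subject variation.

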Participants will be followed with visits scheduled at baseline, 4 weeks, 8 weeks and 12 weeks. At each visit, participants will complete surveys regarding the severity of AKN's associated symptoms (pain, pruritus, burning etc.) as well as the dermatology quality of life index (DLQI) and numerical rating scale (NRS) surveys (Appendix B&D). In addition, photographs will also be obtained for global assessment and lesion count will be performed. The investigator will assess the treatment area for any dyspigmentation and document the % area affected within the treatment area at each visit. Tape strips will also be collected from lesional (occipital scalp) and non-lesional (frontal scalp) at Baseline and Week 12. There will be a phone call visit at week 5 to assess tolerance of medication increase and a safety follow-up visit at Week 14. Statistical analysis will be performed. Throughout the length of the study, any adverse events (AEs) related to the treatment will be recorded.

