## Appendix A.

### Schedule of Events

	Screening	Baseline	W4	W5 c	W8	W12	W14 d	ET
Visit number	1	1 a	2	3	4	5	6	TBD
Informed consent	X							
Medical History	X							
Demographics	X							
Inclusion/Exclusion	X	X						
Concomitant Medications	X	X	X	X	X	X	X	X
Adverse Events	X	X	X	X	X	X	X	X
Pregnancy Test b	X	X	X		X	X		X
Administer IP		X						
Assess IP Compliance			X	X	X	X		
Return IP						X		X
DLQI		X	X		X	X		X
NRS		X	X		X	X		X
AKN severity		X	X		X	X		X
Clinical Photographs		X	X		X	X		X
Clinical Assessment/ Lesion Count		X	X		X	X	X	X
Tape strips (lesional & non- lesional)		X						
Tape strips (lesional only)						X		

- a. If screening is successful, patient will continue into their Baseline visit on same day.
- b. Where applicable, a urine pregnancy test with high sensitivity to HCG will be performed at screening and at all other visits, prior to dosing female participants of childbearing potential with Investigational Product (IP).
- c. Phone call visit
- d. Follow up visit

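### The supplementary lesion-count model leaves its visits undefined and has no time-by-treatment term, so read literally it averages the off-treatment Week 14 count into a single group effect

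*Combined protocol and SAP*

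**What the plan says.** All references are to the combined protocol and SAP.

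- **Data Analysis, Primary Endpoint.** The primary Wilcoxon test (before versus after treatment) and the between-arm Z-test on proportions are both set at 12 weeks. A further Poisson mixed model is then described as "including time and treatment group as fixed factors and a random intercept for each subject". Its span is given only as: "This model will include the whole time-course and contrasts of interests will be estimated". No visits are listed and no contrast is named.
- **Data Analysis, Secondary Endpoints.** The other outcomes are compared "between time points (Baseline, 4, 8, and 12 Weeks"), and their model is a "generalized linear mixed-effects model including time, treatment group, their interaction as fixed effects". Here both the visits and the interaction are stated.
- **Appendix A, Schedule of Events.** The row "Clinical Assessment/ Lesion Count" is marked at Baseline, Weeks 4, 8, 12 and 14, and early termination. The row "Clinical Photographs" is marked at the same visits except Week 14. Study drug is returned at Week 12, or at early termination.
- **Study Design Overview.** "Participants will be followed with visits scheduled at baseline, 4 weeks, 8 weeks and 12 weeks". Week 14 is mentioned separately, as "a safety follow-up visit at Week 14".

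**The concern.** A model with time and group main effects has one treatment coefficient, shared by every visit in the data. If the Week 14 count is among those visits, the coefficient depends partly on what lesions do in the two weeks after drug is returned. It would also cover a longer period than the symptom and quality-of-life models beside it, which stop at Week 12.

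This matters although the model is supplementary. The Wilcoxon test compares pre- and post-treatment counts, and the Z-test compares only the proportions of patients with any reduction. The mixed model is therefore the only planned analysis that compares the size of the lesion-count change between arms, which is what the primary hypothesis is about. Two analysts could follow the present text, choose different visits and report different effects.

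**Working it through.** **The plan's own figure.** The plan gives no figure for this model. Its stated n = 20 belongs to the Wilcoxon test and reproduces: a one-sided 5% paired t-test with difference 0.35 × 15 = 5.25, SD 7 and 80% power needs 13; 13 / 0.955 = 13.6, rounded up to 14; 14 / 0.70 = 20. The point below does not depend on it.

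**Inputs from Sample Size Considerations.** Baseline mean of 15 lesions and a 35% reduction at Week 12, so 15 × 0.65 = 9.75 lesions and ln 0.65 = −0.43.

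**Assumptions not in the documents.** All visits are complete; the effect builds up in equal steps to Week 12; placebo stays at 15 unless stated; the share of the effect still present at Week 14 is 0, one half or all.

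**Check 1: average of visit-specific log rate ratios, baseline included.** Values are 0 at baseline, −0.14 at Week 4, −0.29 at Week 8 and −0.43 at Week 12.

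- Without Week 14: −0.86 / 4 = −0.215.
- Week 14 effect lost (0): −0.86 / 5 = −0.172, 20% smaller.
- Half kept (−0.215): −1.075 / 5 = −0.215, no change.
- All kept (−0.43): −1.29 / 5 = −0.258, 20% larger.

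**Check 2: Poisson fit with time and group main effects to expected counts.** The random intercept was left out of this fit. With complete visits the group rate ratio is total active count divided by total placebo count. Active means are 15, 13.25, 11.5 and 9.75, total 49.5; placebo total is 4 × 15 = 60.

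| Visits in the model | Active total | Placebo total | Group rate ratio |
|---|---|---|---|
| Baseline, 4, 8, 12 | 49.5 | 60 | 0.825 |
| plus Week 14, all kept (9.75) | 59.25 | 75 | 0.790 |
| plus Week 14, half kept (12.375) | 61.875 | 75 | 0.825 |
| plus Week 14, effect lost (15) | 64.5 | 75 | 0.860 |

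On the log scale, −0.192 without Week 14 becomes −0.236 (all kept, about 23% larger) or −0.151 (lost, about 22% smaller). This agrees with Check 1 to within a few percentage points.

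**Sensitivity to a placebo response.** Both arms are assumed to rebound by the same share.

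- Placebo falls 10% by Week 12: 49.5 / 57 = 0.868 without Week 14; 59.25 / 70.5 = 0.840 to 64.5 / 72 = 0.896 with it.
- Placebo falls 20%: 49.5 / 54 = 0.917 without; 59.25 / 66 = 0.898 to 64.5 / 69 = 0.935 with it.

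**Effect of the missing interaction.** With placebo flat, the Week 12 ratio is 9.75 / 15 = 0.65. The main-effects model on Baseline to Week 12 alone gives 0.825, because baseline and the early visits are averaged in. On the log scale that is −0.192 against −0.431, so 1 − 0.192 / 0.431 = 55% of the Week 12 effect is averaged away. When categorical time-by-treatment terms are added, the fitted Week 12 ratio is 0.65 whether or not Week 14 is in the data.

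**The case against.** The best case for the plan is that Week 14 was never meant to enter. The trial is described as lasting 3 months, the follow-up visits are listed to Week 12, Week 14 is labelled a safety visit, both preceding analyses are set at 12 weeks, and the Secondary Endpoints section stops at Week 12. On that reading the whole time-course simply means every visit to Week 12, in contrast to the two-time-point Wilcoxon test. The Week 14 mark also sits in a row that combines clinical assessment with lesion count, so it might refer to the assessment alone. Omitting the interaction may be a slip, since contrasts are promised and the next section includes the term.

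Much of this stands. A reader might infer that the plan commits to pooling off-treatment counts; the documents do not say so. A reader might also infer, from the absence of photographs at Week 14, that counts are obtained differently there. That is not shown. The Endpoints section says counts are captured by photography, but the Study Design Overview can be read as a separate clinical count with photographs for global assessment. All that follows is that no photograph is scheduled to accompany a Week 14 count.

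What does not fall away is that no sentence excludes Week 14 from the model, the schedule marks a count there, and the model as specified would absorb it into its one group effect. The objection that removing Week 14 alone would leave the larger distortion in place is also right, and the fix has to cover both.

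**Conclusion.** The point holds as a conflict between sections, not as a demonstrated pooling of off-treatment data. On a literal reading Week 14 enters the model; on the Study Design Overview's description it need not.

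If it enters, with baseline in the model, the log rate ratio shifts by about a fifth in either direction, or not at all if half the effect persists. In absolute terms the group rate ratio moves from 0.825 to between 0.790 and 0.860. These figures rest on complete visits, a steady build-up to the plan's 35% reduction, a flat placebo arm and an assumed retained share; with a placebo response the shifts in the ratio are smaller. The direction cannot be known in advance. It would be wrong to conclude that Week 14 must dilute the effect.

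The missing interaction is the larger problem, turning 0.65 into 0.825 without any Week 14 data. Only the supplementary model is affected: the Wilcoxon test, the Z-test and the sample size stand as they are. The change should be made, but it is not critical.

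**What to change.** In Data Analysis, Primary Endpoint:

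1. Replace the reference to the whole time-course with an explicit list: Baseline and Weeks 4, 8 and 12, matching Secondary Endpoints. Say in the same place how early-termination counts, which are also scheduled, are handled.
2. Add the time-by-treatment interaction, with time as a categorical factor, as the secondary-outcome models already include an interaction.
3. Name the Week 12 between-group contrast as the one of interest.
4. Report the Week 14 count separately by arm as off-treatment follow-up.

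The cost is a few lines of wording. No visit, patient or measurement changes. The only downside is that Week 14 counts no longer contribute to the model; they are still collected and reported.
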